### **7.5.3 Vital Signs**

A table summarizing clinically notable blood pressure and weight measurements which are aligned with CTCAE cut-offs, where available, will be displayed. The proportion of subjects whose worst observed values while on study (on or after the first day of treatment) meet the following clinically notable criteria will be tabulated by treatment arm:

- Systolic Blood Pressure
  - < 85 mm Hg
  - $\geq 140$  - < 160 mm Hg
  - $\geq 160$  mm Hg
- Diastolic Blood Pressure
  - < 50 mm Hg
  - $\geq 90$  - < 100 mm Hg
  - $\geq 100$  mm Hg
- Weight gain from baseline
  - $\geq 5\%$  - < 10% increase
  - $\geq 10\%$  - < 20% increase
  - $\geq 20\%$  increase
- Weight loss from baseline
  - $\geq 5\%$  - < 10% decrease
  - $\geq 10\%$  - < 20% decrease
  - $\geq 20\%$  decrease

Vital signs will be listed by patient.

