- 3 Outpatient assessments should be based on weekly telephone/videoconference communication with the patient to document an evaluation of the **daily** 7-point ordinal scale score for the days between contacts confirmation of pacritinib/ placebo dosing if continuing on treatment as an outpatient, AEs, and the use of concomitant medications. More frequent telephone/videoconference contact may occur as needed to supplement the above assessments. Review of medical records may also be performed as needed to supplement these assessments; medical records should be reviewed for patients who cannot be reached by telephone/videoconference.
- 4 Vital signs include blood pressure, pulse, respiratory rate, temperature, SpO2, and body weight.
- 5 The 7-point ordinal scale of clinical status is as follows: category 7 = death; 6 = hospitalization, requiring IMV and/or ECMO; 5 = hospitalization, on non-invasive positive pressure ventilation or high-flow nasal cannula; 4 = hospitalization, requiring supplemental oxygen not meeting the criteria for categories 5 or 6; 3 = hospitalization, not requiring supplemental oxygen; 2 = not hospitalized but unable to resume normal activities; 1 = not hospitalized with resumption of normal activities.
- 6 Any physical examination performed as part of routine care on Day 1 prior to signing of informed consent may be used for documentation

- 7 ECG will be performed at Screening (may be performed within 48 hours prior to the start of Screening), Day 3, Day 8, Day 15 or EOT, Day 22, Day 28, and on the day of hospital discharge if before EOT. ECGs are not required after hospital discharge but must be performed on the day of discharge if the patient will be continuing pacritinib/placebo as an outpatient. Results from unscheduled ECG assessments should be entered into the electronic database using an Unscheduled ECG CRF. ECGs should be assessed using at least 3 leads; rhythm strips from telemetry monitoring are acceptable.

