#### **7.1.4 *Summary of Study Assessments and Events by Day***

##### **7.1.4.1 *Screening (Study Day -1 or 1)***

The Screening evaluations listed below are to be carried out between Day -1 and Day 1 (prior to the start of treatment). Screening and randomization may occur on either Day -1 or Day 1. Patients may be screened, randomized, and started treatment on the same day (Day 1).

- Signing of ICF within 96 hours after hospital admission
- Demographics (age, sex, race, and ethnicity)
- Medical history
- Vital signs (blood pressure, pulse, respiratory rate, temperature, SpO2, and body weight)
- 7-point ordinal scale of clinical status
- SpO2 in ambient air (if possible)

- SpO2 with oxygen supplementation (if applicable)
- Highest %FiO2 (if on CPAP, BiPAP, or IMV)
- Highest PEEP)( if on positive pressure ventilation)
- ECG (at least 3 leads; may be performed within 48 hours prior to the start of Screening)
- Serum chemistry, including sodium, potassium, chloride, bicarbonate, blood urea nitrogen, creatinine, glucose, calcium, and magnesium (The results of laboratory assessments performed in the emergency room [ER] or upon hospital admission that are relevant for the determination of eligibility may be used to confirm eligibility provided that they have been performed within 24 hours prior to the start of Screening.)
- Liver function panel, including aspartate aminotransferase (AST), alanine aminotransferase (ALT), alkaline phosphatase (ALP), total bilirubin, and albumin (The results of laboratory assessments performed in the ER or upon hospital admission that are relevant for the determination of eligibility may be used to confirm eligibility provided that they have been performed within 24 hours prior to the start of Screening.)
- CBC, including WBC count, hemoglobin, hematocrit, and platelet count (The results of laboratory assessments performed in the ER or upon hospital admission that are relevant for the determination of eligibility may be used to confirm eligibility provided that they have been performed within 24 hours prior to the start of Screening.)
- WBC differential (The results of laboratory assessments performed in the ER or upon hospital admission that are relevant for the determination of eligibility may be used to confirm eligibility provided that they have been performed within 24 hours prior to the start of Screening.)

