## **8.3 Vital Signs and Physical Examination**

Vital signs (blood pressure, pulse, respiratory rate, temperature, SpO2, and body weight) and physical examinations will be obtained at Screening.

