### **5.2.3 Vital Signs**

Vital signs will be assessed at the times specified in protocol Table 1. The vital signs assessment will include recording of the systolic blood pressure (mmHg), diastolic blood pressure (mmHg), respiratory rate (breaths/minute), maximum temperature, maximum heart rate, SpO2, and body weight.

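### SAP 7.5.3 tabulates worst on-study blood pressure and weight change by arm, but the protocol schedules both only at Screening, before the first dose

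*SAP*

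**What the plan says.** **What the SAP will report.** SAP 7.5.3 commits to one vital-signs table: "A table summarizing clinically notable blood pressure and weight measurements which are aligned with CTCAE cut-offs, where available, will be displayed". The value used is the patient's "worst observed values while on study (on or after the first day of treatment"), tabulated by treatment arm. There are three categories each for systolic pressure, diastolic pressure, weight gain and weight loss. The section ends with a by-patient listing of vital signs.

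**Where the SAP takes its timing.** SAP 5.2.3 sets no schedule of its own: "Vital signs will be assessed at the times specified in protocol Table 1". It counts maximum temperature and maximum heart rate as vital signs, alongside blood pressure, respiratory rate, SpO2 and weight.

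**What the protocol collects.** The vital-signs row of Table 1 has a single mark, in the Screening column. Footnote 4 ("Vital signs include blood pressure, pulse, respiratory rate, temperature" and so on) goes on to include SpO2 and body weight, so blood pressure and weight exist in the schedule only as parts of this item. Protocol 8.3 says vital signs "and physical examinations will be obtained at Screening". Protocol 7.1.4.1 fixes when that is: "The Screening evaluations listed below are to be carried out between Day -1 and Day 1 (prior to the start of treatment").

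**The concern.** The table is meant to show whether blood pressure or weight moves under treatment, and for that it needs values taken after dosing. The schedule that the SAP relies on provides none.

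The main risk is a misleading table. The reporting window opens on a calendar day, not at the first dose, and Screening may fall on that day. A pre-dose reading could then be printed as an on-study safety result. SAP 7.5 produces safety summaries for the Safety Population, and 7.5.3 names no other denominator. Patients with no post-dose value could therefore count silently as not meeting any criterion. A row of zeros would look like reassurance when it only reflects that nothing was scheduled.

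Meanwhile, two vital signs that are recorded repeatedly after baseline, Tmax and HRmax, have no by-arm summary in the plan.

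**Working it through.** The point rests on no sample size, power or alpha figure. The check sets the planned table against the collection schedule.

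**1. What the table needs.** SAP 7.5.3: 3 systolic + 3 diastolic + 3 weight-gain + 3 weight-loss = 12 categories per arm. The blood pressure rows need at least one on-study value per patient. The weight rows need a baseline and a later value.

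**2. What each protocol list schedules.**

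| Protocol location | Blood pressure and weight scheduled? |
|---|---|
| 7.1.4.1 Screening (Day -1 or Day 1, before treatment) | Yes, once |
| 7.1.4.3 Day 1 pre-dose | No |
| 7.1.4.4 Days 2 to 28 | No |
| 7.1.4.5 End of Treatment | No |
| 7.1.4.6 30-day follow-up | No |
| 7.1.4.7 Hospital discharge | No |
| 7.1.4.8 Outpatient | No |

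The Table 1 row agrees with these lists: one mark, at Screening. Because the visit lists and the table agree independently, the single mark is not an artefact of how the table was read.

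**3. Count per patient.** Scheduled blood pressure values: 1. Scheduled weights: 1. SAP 7.1.1 takes baseline as the last value before treatment starts, so that one value is the baseline. Scheduled post-dose values: 1 - 1 = 0 for each, and so 0 across the roughly 200 planned patients.

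**4. Weight rows.** There is no scheduled second weight. If a Day 1 Screening weight w is let into the window, it is compared with itself: (w - w)/w = 0%. That falls in none of the six categories, the smallest of which starts at 5%.

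**5. Blood pressure rows.** SAP 7.1.1 makes Study Day 1 the day of first dose. Under the 7.5.3 window:
- Screened on Day 1: the pre-dose Screening pressure falls inside the window and is counted as on-study.
- Screened on Day -1: the same kind of reading falls outside, and the patient has no scheduled value.

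The documents do not give the share screened on Day 1. Over the possible range of 0% to 100%, scheduled values in these rows number from 0 to about 200, and every one of them is pre-dose. A comparison of arms on pre-dose values cannot show a drug effect.

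**6. What is collected after baseline.** Table 1 and 7.1.4.4 record Tmax daily on Days 2 to 28 and HRmax daily on Days 2 to 14, both also at EOT and discharge. The Day 1 entries for both cover the 24 hours before dosing (7.1.4.3), so post-dose values begin on Day 2. In the SAP, baseline fever and tachycardia may be summarised (7.2.2) and vital signs are listed (7.5.3). No post-baseline summary of Tmax or HRmax by arm is planned.

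**The case against.** **The table may not be empty.** A reader might infer that it simply cannot be filled. The documents do not support that: as step 5 shows, the window as worded can admit a Day 1 Screening blood pressure. This objection stands, but it does not rescue the table, because it replaces a blank with a baseline reading labelled as on-study.

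**Values could come from elsewhere.** Physical examinations are scheduled on Days 8, 15, 22 and 28, at EOT and at discharge. Their content is not specified and the eCRF is not among the documents, so blood pressure or weight might be captured there. A reader might equally infer that any entries would be selective, unscheduled ones. That is conjecture: the protocol names unscheduled forms for laboratory tests, ECG and disease markers, and none for vital signs. What can be said is that no post-dose value is required.

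**Protocol 8.3 may not mean Screening only.** The same sentence places physical examinations at Screening, yet Table 1 puts them on Day 1 and later. Taken alone, 8.3 is weak evidence of exclusivity. Table 1 and the visit lists carry the point without it.

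**The collected vital signs are not ignored.** A reader might infer that they go unanalysed. That is too strong: SpO2 is summarised by timepoint (SAP 7.2.5), and vital signs are listed by patient. The gap is limited to by-arm post-baseline summaries of Tmax and HRmax.

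**The stakes are modest.** Clinically significant abnormalities, and those needing intervention, are reportable as adverse events (protocol 8.1.1). TEAEs are summarised by grade, System Organ Class and preferred term, with cardiac events shown separately (SAP 7.5.1). This stands and limits the consequence, but it gives no reason to keep a table that the schedule does not feed.

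**Conclusion.** The inconsistency is real. As scheduled, the six weight-change rows have no second value for any patient. The six blood pressure rows have no post-dose value and could hold only pre-dose readings, from a subset of patients defined by the day they were screened. Tmax and HRmax have post-baseline data and no planned by-arm summary.

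This rests on Table 1 and the visit lists being the full schedule. It could change only if the eCRF collects blood pressure or weight after dosing without the protocol saying so, which cannot be checked from the documents.

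The defect lies in one descriptive safety table. It touches no hypothesis test, no stopping rule and no efficacy conclusion. It is worth correcting because the table as specified could be misread as evidence that blood pressure and weight were monitored on treatment.

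**What to change.** **SAP wording only (preferred).**
- Remove the blood pressure and weight-change table from 7.5.3. Alternatively, keep it but limit it to values recorded after the first dose, use the number of patients with such a value as the denominator, and print that number by arm.
- Add a by-arm summary of worst post-first-dose Tmax and HRmax. State the windows: Tmax daily on Days 2 to 28, HRmax daily on Days 2 to 14, both plus EOT and discharge. Exclude the Day 1 entries, which cover the 24 hours before dosing.
- Record the change in SAP section 9, which now states that no changes are planned.

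The cost is a few lines of SAP text and one revised table shell. No new data are needed, because Tmax and HRmax are already collected.

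**Alternative.** Add post-baseline blood pressure and weight to Table 1 and the eCRF. This is a protocol amendment and needs IRB/REB/IEC approval before sites can use it (protocol section 16). The SAP is dated 13 September 2021 and written against Amendment 4; enrolment status is not in the documents. Patients already treated would need retrospective chart abstraction, and outpatients, who are followed by telephone or video, would still have no scheduled measurements. This route makes sense only if enough enrolment remains to justify it.

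In either case, reconcile the placement of the physical examination between protocol 8.3 (Screening) and Table 1 (Day 1 and later).

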#### **7.5.4      *Electrocardiograms***

The frequency distribution of abnormal mean QTcF interval measurements on study (after the first study drug treatment through the last dose of study drug) will be summarized. That is, the proportion of subjects with the worst mean QTcF interval on study will be reported, and the following QTcF intervals will be tabulated by treatment arm:

- A measured value
  - > 450 ms
  - > 480 ms
  - > 500 ms
- Change
  - > 0 and  $\leq 10$  ms above baseline
  - > 10 and < 20 ms above baseline
  - $\geq 20$  ms above baseline

- > 30 ms above baseline
- > 60 ms above baseline

Plots of the QTcF across study day (Day8, Day 15, Day 22 and Day28 )will also be presented for each treatment arm.

ECG assessments including clinical significance will be listed by patient.

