The majority of non-hematologic AEs was mild or moderate in severity, and rates were generally similar across dosing arms with the exception of gastrointestinal events, which occurred more commonly in patients treated at 200 mg BID (39/54, 72.2%) than in patients treated at lower doses (100 mg QD: 26/52, 50.0%; 100 mg BID: 30/55, 54.5%). These events were largely grade 1 or 2 and usually occurred within the first 8 weeks on treatment. Diarrhea was common but generally manageable with standard antidiarrheal agents and tended to be short-lived: the median duration of pacritinib-related diarrhea was 2 weeks. The most common hematologic AEs were thrombocytopenia and anemia, both of which occurred more frequently in patients treated at 200 mg BID (40.7% and 24.1% respectively). Cardiac events were more common in patients treated at 200 mg BID (40.7%, n = 22) than in patients treated at lower doses (100 mg QD: 21.2%, n = 11; 100 mg BID: 21.8%, n = 12) but were largely grade 1 or 2 in severity, with the most common being peripheral edema (200 mg BID: 16.7%) and QT prolongation (200 mg BID: 7.4%). There was no excess in grade 3 or 4 cardiac events in patients treated at the highest dose (100 mg QD: 5.8%, n = 3; 100 mg BID: 5.5%, n = 3; and 200 mg BID: 3.7%, n = 2; no grade 4 events). The mean change in corrected QT interval (QTc) between Baseline and Week 24 was roughly +10 msec on all arms; no patient had a QTc > 500 msec. Bleeding events were more common in patients treated at 200 mg BID (42.6%, n = 23) than in patients treated at lower doses (100 mg QD: 36.5%, n = 19; 100 mg BID: 25.5%, n = 14) but were largely grade 1 or 2 in severity, with the most common being epistaxis (200 mg BID: 14.8%) and bruising (200 mg BID: 9.3%). There was no excess in grade 3 or 4 bleeding events in patients treated at the highest dose (100 mg QD: 7.7%, n = 4; 100 mg BID: 3.6%, n = 2; and 200 mg BID: 5.6%, n = 3; no grade 4 events). The rate of fatal events was similar across all arms: 100 mg QD: 7.7%, n = 4 (sepsis, disease progression, tuberculosis, and general state deterioration); 100 mg BID: 5.5%, n = 3 (myelofibrosis, subdural hemorrhage, and heart failure); and 200 mg BID: 5.6%, n = 3 (sepsis, respiratory failure, and subdural hematoma).

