### **5.2.4 Electrocardiograms (ECGs)**

The ECG assessment will be performed at the times specified in protocol Table 1.

The Fridericia-Corrected QT interval (QTcF) and overall interpretation will be recorded.

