### 7.1 General Statistical Considerations

Unless specified otherwise, the analyses of data collected will be descriptive and summaries will be presented separately for each treatment arm and in total for the specified analysis population. Statistical analyses will be descriptive and no formal hypothesis testing or comparative analyses between treatment arms will be performed unless stated. Confidence intervals (CIs) will be constructed at the 95% confidence level where appropriate. For categorical variables, confidence intervals will be calculated using the Clopper-Pearson method where appropriate.

For continuous variables, the number of observations (n), mean, standard deviation, median, q1, q3, minimum, and maximum will be provided as summary statistics. For categorical variables, the frequency and percentage in each category will be displayed.

Summary tables will in general display 2 treatment arms:

- Pacritinib 400 mg
- Placebo

A total column will be added for table summaries if appropriate.

Efficacy analyses will in general be based on the ITT Population according to the randomized (planned) treatment arm.

Safety analyses will in general be performed using the Safety Population according to the treatment actually received.

Subject disposition, demographics, and clinical baseline characteristics data will be summarized for the ITT Population. If the ITT Population differs from other defined analysis populations, additional patient characteristic summaries may be generated using other analysis populations.

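### SAP 7.5.4 counts QTcF outliers by arm but specifies no mean change and no between-arm difference, so the size of any drug effect is not estimated and precision is lost

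*SAP*

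**What the plan says.** SAP 5.2.4 has QTcF captured as a measured interval: "The Fridericia-Corrected QT interval (QTcF) and overall interpretation will be recorded". Protocol Section 6.5.4 schedules ECGs at Screening and on Days 3, 8, 15 (or end of treatment), 22 and 28, and on the day of discharge for patients who continue study drug at home. Protocol Section 3 does not require ECGs after discharge.

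The summary planned in SAP 7.5.4 is "The frequency distribution of abnormal mean QTcF interval measurements on study". It reduces each patient to one worst value: "the proportion of subjects with the worst mean QTcF interval on study will be reported". The window is "after the first study drug treatment through the last dose of study drug". The rows are:

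- worst value >450, >480 and >500 ms;
- change >0 to ≤10 ms, "> 10 and < 20 ms above baseline", ≥20 ms, >30 ms and >60 ms.

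The section also promises "Plots of the QTcF across study day" for each arm at Days 8, 15, 22 and 28, without saying what is plotted, and a listing. The word mean in this section qualifies each patient's QTcF reading. The output is a frequency table, so it is not an arm mean.

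Two other places bear on the point. SAP 7.1 has a general rule: "For continuous variables, the number of observations (n), mean, standard deviation, median, q1, q3, minimum, and maximum will be provided as summary statistics". It also says that arms are not formally compared unless this is stated, and nothing is stated for QTcF. SAP 7.5.2 explicitly plans values and changes from baseline by visit for laboratory parameters. SAP 7.5.4 has no matching sentence.

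**The concern.** QT prolongation is a named risk of the drug (Protocol 6.5.2) with its own dose-management table (Protocol Table 4). The earlier evidence in the Protocol is the PAC203 overview, where the mean QTc change "between Baseline and Week 24 was roughly +10 msec on all arms; no patient had a QTc > 500 msec". That study compared three pacritinib doses without a placebo arm, so it cannot separate a drug effect from other causes of change. This trial can: randomisation balances illness and co-medication between the arms.

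The planned table does not use that strength. It gives neither the size of a pacritinib-minus-placebo shift nor its precision. A modest shift moves few patients across 480 or 500 ms or beyond +60 ms, so similar counts in those rows could be read as reassurance about a quantity that was never estimated.

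**Working it through.** **Inputs.** The documents state no power or precision for QTcF. From them come about 200 patients randomised 1:1 (SAP 3.4), the row limits (SAP 7.5.4) and the ECG days (Protocol 6.5.4). Assumed, because the documents do not give them: SD of individual QTcF change 15–30 ms, the share of patients still having ECGs, and a between-arm difference of 10 ms. A two-sided 5% test is used only as a yardstick, since no safety test is planned.

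**1. The plan's own figure.** For 26.5% vs 13.5%, one-sided 0.10 and 80% power:
n = [1.2816·√(2·0.20·0.80) + 0.8416·√(0.265·0.735 + 0.135·0.865)]² / 0.13² = (0.7250 + 0.4698)² / 0.0169 ≈ 84.5, so 85 per arm.
With continuity correction, (84.5/4)·[1 + √(1 + 4/(84.5·0.13))]² ≈ 99.3, so 100 per arm. The stated 200 is reproduced, and 100 per arm is used below.

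**2. Precision of a mean difference.** Half-width of the 95% CI = 1.96·SD·√(2/n).
- n = 100: 4.2, 5.5, 6.9, 8.3 ms at SD 15, 20, 25, 30.
- n = 50: 5.9, 7.8, 9.8, 11.8 ms.

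**3. One normal change per patient (closed form).** Power for the mean = Φ(10/(SD·√(2/n)) − 1.96). At SD 20 and n = 100: 10/2.83 = 3.54, and Φ(1.58) = 94%. For the ≥20 ms row at SD 20, control P(Z > 1) = 15.9% and pacritinib P(Z > 0.5) = 30.9%, which gives power 71%. For 80% power, the best single cut needs 59, 102, 158 and 226 per arm at SD 15, 20, 25 and 30, where the mean needs 36, 63, 99 and 142. That is about 1.6 times as many patients.

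**4. Worst value, as the SAP uses it (simulation).** Every patient has a Day 3 ECG and 70% have a Day 8 ECG, with correlation 0.5 and control mean change 0. The worst change is the larger of the two. Simulation error is one to two points.

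| Power, 10 ms difference, 100 per arm | SD 15 | SD 20 | SD 25 | SD 30 |
|---|---|---|---|---|
| Mean change, Day 3 only | 100% | 94% | 80% | 64% |
| ≥20 ms (planned row) | 94% | 79% | 64% | 51% |
| >10 ms (reader must add two planned rows) | 98% | 85% | 66% | 51% |
| >30 ms (planned row) | 74% | 69% | 56% | 46% |

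The >60 ms row has 0–19% across these SDs. The mean gains 100−94 = 6, 94−79 = 15, 80−64 = 16 and 64−51 = 13 points over the ≥20 ms row. The two lowest bands are disjoint and hardly move on their own: at SD 20, >0 to ≤10 ms goes from 21% to 18% of patients, and >10 to <20 ms from 18% to 21%.

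**5. Absolute limits.** Closed form, with an assumed placebo mean of 420–440 ms and SD of 25–30 ms: power is 37–61% for >450 ms, 13–33% for >480 ms and 5–16% for >500 ms.

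**6. Fewer ECGs.** With 50 per arm (closed form) the mean has 92, 71, 52 and 39%, and the best single cut has 73, 50, 35 and 26%.

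**7. Do other outputs fill the gap?** The plots omit Day 3. Dosing ends at Day 14, or at Day 21 if extended, so Days 22 and 28 are off treatment in either case. The SAP 7.1 rule says which statistics accompany a continuous summary. It does not say that a QTcF change table exists, at which visits, or with what between-arm contrast.

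**The case against.** The strongest reply is that this is a gap in detail and not a decision to discard the mean. SAP 7.1 already prescribes n, mean and SD for continuous variables, SAP 7.5.4 promises plots by arm, and cardiac arrhythmia events are summarised separately. The safety analysis is descriptive throughout, so power is not its criterion. Counts of worst QTcF are an outlier screen that includes the >500 ms limit used in Protocol Table 4, and vital signs are handled in the same way. This stands in part. The omission may be unintended, and the category table serves a proper purpose. But nothing quoted commits anyone to producing a QTcF change by visit, and SAP 7.5.2 shows that the authors wrote such a commitment where they meant one.

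A reader might infer that a 10 ms shift would probably be missed. The documents do not support that. The table contains a ≥20 ms row, which at 100 per arm detects such a shift with 51–94% power over the assumed SDs. Where the categories become weak, with large SDs and few patients still having ECGs, the mean is weak too (52% and 39% at 50 per arm with SD 25 and 30).

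A reader might also take the PAC203 figure as the drug's effect. It is a within-arm change at Week 24 in myelofibrosis, similar at all three doses and without a placebo control. It is a guide to size only.

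Finally, adjusting the difference for baseline QTcF would depart from SAP 7.1.2, which plans no adjustment for other covariates. That is correct and is dealt with in the fix.

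**Conclusion.** The point holds in a limited form. SAP 7.5.4 specifies no mean QTcF change by visit and arm and no between-arm difference with an interval, so the planned outputs do not estimate the size of a drug effect that this trial is designed to isolate. The loss of precision is moderate: 6–16 power points against the best row the table prints, or about 1.6 times the patients for equal power from the best single cut. It is large only against the alert limits (>480, >500 and >60 ms). These sizes rest on assumed SDs of 15–30 ms, 100 per arm with ECGs and an illustrative 10 ms difference. The absence of an estimate rests on none of them.

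**What to change.** In SAP 7.5.4, add a descriptive table for the Safety Population giving n, mean and SD of QTcF and of its change from baseline, by arm, at each scheduled on-treatment ECG including Days 3 and 8. Add the pacritinib-minus-placebo difference in mean change with a 95% CI. State whether a Day 15 ECG taken after Day 14 dosing counts as on treatment, since the present window closes at the last dose. Use the unadjusted difference or, if it is adjusted for baseline QTcF, record that as an exception to SAP 7.1.2. Add Day 3 to the plots and name the plotted statistic. Keep the threshold and change-category table as the outlier analysis.

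The cost is one paragraph and one table from data already collected. No visit, ECG or dosing rule changes. The limitation to state beside the table is that later visits rest on patients still in hospital, so the interval widens from about 4–8 ms at 100 per arm to about 6–12 ms at 50 per arm, and the remaining patients are a selected group.
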